8.2 Dose Modifications of Lenalidomide during a Cycle of Therapy

Dose reductions of one drug and not the other may be done at the investigators discretion based on attribution of adverse events except neutropenia in which lenalidomide should be decreased first before anakinra.

→ → Use the NCI Common Terminology Criteria for Adverse Events (CTCAE) version 4.0* unless otherwise specified ← ←

CTCAE System/Organ/Class (SOC)	ADVERSE EVENT	AGENT	ACTION** Days 2-14 of cycle	ACTION** Day ≥15 of cycle
Blood and lymphatic system disorders	Febrile neutropenia associated with fever (temperature ≥38.5°C)	Lenalidomide	Omit lenalidomide dose. Follow CBC weekly. If neutropenia has resolved to ≤Grade 2 prior to Day 21, restart lenalidomide at next lower dose level and continue the cycle through Day 21. If neutropenia is the only toxicity for which a dose reduction is required, G-CSF may be used and the lenalidomide dose maintained	Omit lenalidomide for remainder of cycle. See Section 8.11 for Initiation of a New Cycle and reduce the dose of lenalidomide by 1 dose level. If neutropenia is the only toxicity for which a dose reduction is required, G-CSF may be used and the lenalidomide dose maintained for the next cycle at the investigator's discretion.
Investigations	Platelet count decreased ≥ Grade 3 (platelet count <50,000/mm ³)	Lenalidomide	Omit lenalidomide dose Follow CBC weekly Hold anticoagulation until platelets >50,000 If thrombocyte-penia resolves to ≤Grade 2 prior to Day 21, restart lenalidomide at next lower dose level and continue the cycle through Day 21	Omit lenalidomide for remainder of cycle See Section 8.11 , Instructions for Initiation of a New Cycle and reduce the dose of lenalidomide by 1 dose level

CTCAE System/Organ/Class (SOC)	ADVERSE EVENT	AGENT	ACTION** Days 2-14 of cycle	ACTION** Day \geq 15 of cycle
Skin and subcutaneous tissue disorders	Rash maculo papular Grade 2 or 3.	Lenalidomide	Omit lenalidomide dose Follow weekly If the event resolves to \leq Grade 1 prior to Day 21, restart lenalidomide at next lower dose level and continue the cycle through Day 21	Omit lenalidomide for remainder of cycle See Section 8.11 , Instructions for Initiation of a New Cycle and reduce the dose of lenalidomide by 1 dose level
	Any rash Grade 4	Lenalidomide	Discontinue lenalidomide	Discontinue lenalidomide
Nervous System Disorders	Peripheral sensory neuropathy Grade 3	Lenalidomide	Omit lenalidomide dose Follow at least weekly If the event resolves to \leq Grade 1 prior to Day 21, restart lenalidomide at next lower dose level and continue the cycle through Day 21	Omit lenalidomide for the remainder of the cycle. See Section 8.11 Instructions for Initiation of a New Cycle and reduce the dose of lenalidomide by 1 dose level
	Peripheral sensory neuropathy Grade 4	Lenalidomide	Discontinue lenalidomide	Discontinue lenalidomide
Immune system disorders	Allergic reaction Grade 2-3	Lenalidomide	Omit dose Follow at least weekly If the toxicity resolves to \leq Grade 1 prior to Day 15 restart at next lower dose level and continue the cycle until Day 21	Omit lenalidomide for the remainder of the cycle If the adverse event resolves to \leq Grade 1, reduce dose 1 level in next cycle If adverse event recurs, discontinue therapy
	Grade 4	Lenalidomide	Discontinue lenalidomide	Discontinue lenalidomide
Vascular disorders	Thromboembolic event \geq Grade 3	Lenalidomide	Omit dose and start anticoagulation; restart at investigator's discretion (maintain dose level)	Omit lenalidomide for remainder of cycle and start anticoagulation. Maintain dose level in next cycle

CTCAE System/Organ/Class (SOC)	ADVERSE EVENT	AGENT	ACTION** Days 2-14 of cycle	ACTION** Day \geq 15 of cycle
Endocrine disorders	Hyperthyroidism or Hypothyroidism \geq Grade 2	Lenalidomide	-Omit lenalidomide for remainder of cycle, evaluate etiology, and initiate appropriate therapy. -See Instructions for Initiation of a New Cycle and reduce the dose of lenalidomide by 1 dose level	Omit lenalidomide for remainder of cycle, evaluate etiology, and initiate appropriate therapy. See Section 8.11 , Instructions for Initiation of a New Cycle and reduce the dose of lenalidomide by 1 dose level
Other non-hematologic adverse event	Other non-hematologic toxicity \geq Grade 3	Lenalidomide	-Omit lenalidomide dose. Follow at least weekly. If the toxicity resolves to \leq Grade 2 prior to Day 21, restart lenalidomide at next lower dose level and continue the cycle through Day 21	Omit lenalidomide for remainder of cycle. See Section 8.11 , Instructions for Initiation of a New Cycle and reduce the dose of lenalidomide by 1 dose level.

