7.22 Definition of DLT – See Section 16.22 for additional information

For this protocol, DLT will be defined as an adverse event during Cycle 1 of treatment at least possibly related to the study medication and meeting the following criteria:

Toxicity*	DLT Definition
Blood and lymphatic system disorders	Grade 3 Febrile neutropenia: ANC <1000/mm ³ with a single temperature of >38.3 degrees C (101 degrees F) or a sustained temperature of ≥38 degrees C (100.4 degrees F) for more than one hour
Investigations	Grade 4 neutropenia (ANC <500/mm ³) for ≥7 days or Grade 4 thrombocytopenia (<25,000/mm ³) for ≥7 days
Infection and infestations	Grade 4
Other Non-hematologic	Grade 4 as per NCI Common Terminology Criteria for Adverse Events v 4.0**
Dose Delay	Any toxicity that causes a dose delay of >2 weeks of the next intended dose.***
Dose Reduction	Any dose reduction within cycle 1.***

*Adverse event at least possibly related to the study medication.

**Grade 4 vomiting or diarrhea with maximal supportive treatment(s) will be considered dose limiting.

***Except dose reductions and delays due to rash associated with lenalidomide. These patients will be replaced with another study patient.

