8.0 Dosage Modification Based on Adverse Events

Strictly follow the modifications in this table for the first **two** cycles, until individual treatment tolerance can be ascertained. Thereafter, these modifications should be regarded as guidelines to produce mild-to-moderate, but not debilitating, side effects. If multiple adverse events are seen, administer dose based on greatest reduction required for any single adverse event observed. Reductions or increases apply to treatment given in the preceding cycle and are based on adverse events observed since the prior dose.

ALERT: *ADR reporting may be required for some adverse events (See Section 10)*

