8.3 Dose Modifications of Anakinra/Placebo during a Cycle of Therapy

Dose reductions of one drug and not the other may be done at the investigators discretion based on attribution of adverse events except neutropenia in which lenalidomide should be decreased first before anakinra.

CTCAE System/organ/Class (SOC)	ADVERSE EVENT	AGENT	ACTION ** (each cycle)
Blood and lymphatic system disorders	Febrile Neutropenia \geq Grade 3	Anakinra/ Placebo	For ANC <1000, omit anakinra/placebo until ANC \geq 1500. Then restart anakinra or placebo with the dose reduced one dose level.
Infections and Infestations	Infection/Febrile Neutropenia \geq Grade 2		Omit until infection resolved; then restart at same dose
	Infection/Febrile Neutropenia \geq Grade 3		Omit until infection resolved; then restart anakinra or placebo with the dose reduced one dose level
Other non-hematologic adverse event	Any adverse event \geq Grade 3		Omit until toxicity reduces to \leq grade 2; then restart anakinra or placebo with the dose reduced one dose level

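### For neutropenia with fever, the lenalidomide and anakinra tables can reduce anakinra while lenalidomide stays unchanged, against the protocol's stated order of reduction

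*Combined protocol and SAP*

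**What the plan says.** Three places in the protocol deal with neutropenia and fever.

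- **Section 7.22 (DLT definition).** The event is "Grade 3 Febrile neutropenia: ANC <1000/mm"³ "with a single temperature of >38.3 degrees C" "or a sustained temperature of ≥38 degrees C (100.4 degrees F) for more than one hour". It counts as a DLT in Cycle 1 if at least possibly related. Grade 4 neutropenia lasting 7 days or more is a separate DLT.
- **Section 8.2 (lenalidomide table).** The one neutropenia row reads "Febrile neutropenia associated with fever (temperature ≥38.5°C". It states no entry ANC and no grade. On Days 2-14 the drug is withheld and then restarted a level lower once neutropenia is Grade 2 or better before Day 21. If neutropenia is the only toxicity calling for a reduction, G-CSF may be given and the lenalidomide dose kept.
- **Section 8.3 (anakinra/placebo table).** For febrile neutropenia of Grade 3 or higher the instruction begins "For ANC <1000, omit anakinra/placebo until ANC" recovers to 1500, after which the drug restarts one level lower. The row has no temperature and no G-CSF option.

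Sections 8.2 and 8.3 open with the same sentence. It leaves single-drug reductions to the investigator, "except neutropenia in which lenalidomide should be decreased first before anakinra". Section 8.0 makes the modifications strict for the first two cycles, "until individual treatment tolerance can be ascertained", and guidelines after that.

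**The concern.** Both drugs can lower neutrophils: section 15.17 lists neutropenia and febrile neutropenia among lenalidomide events at 10% or more, and section 15.37 lists neutropenia at 1% to 10% for anakinra. The protocol recognises the overlap and fixes an order, lenalidomide first. The rows beneath that sentence do not always deliver the order, because the lenalidomide row needs a higher fever than the anakinra/placebo row and because only the lenalidomide row has a G-CSF alternative.

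Two sites following the same pages could manage the same patient in opposite ways. In phase II the reduction falls on the blinded injection. In the experimental arm that is the agent under test; in the control arm it is saline.

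**Working it through.** The plan gives no figure to reproduce on this point, so the check sets the rules side by side and traces patients through them.

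| Rule | ANC at entry | Grade at entry | Fever at entry | Restart condition | Effect on dose level |
|---|---|---|---|---|---|
| 7.22 DLT | <1000 | 3 | single >38.3°C, or ≥38°C for over 1 hour | none | none; defines a DLT |
| 8.2 lenalidomide, Days 2-14 | not given | not given | ≥38.5°C | Grade ≤2 before Day 21 | one level down, or kept with G-CSF |
| 8.3 anakinra/placebo | <1000 | ≥3 | not given | ANC ≥1500 | one level down |

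**Width of the gap.** The event is Grade 3 under 7.22 but misses the lenalidomide row in these ranges:
- single reading: above 38.3 and below 38.5, a width of 38.5 − 38.3 = 0.2°C;
- sustained reading: from 38.0 to below 38.5, a width of 38.5 − 38.0 = 0.5°C.

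**Assumption.** Grade 3 febrile neutropenia in 8.3 means the event that 7.22 labels Grade 3. Section 8.3 supplies no other temperature.

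**Case A: Day 10, ANC 800, single reading 38.4°C.** The 8.2 row is not met (38.4 < 38.5). No other lenalidomide row covers neutrophils, since the catch-all row is for non-hematologic events. The 8.3 row is met (Grade 3, 800 < 1000). Result: anakinra/placebo goes down one level and lenalidomide continues unchanged. The order is reversed.

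**Case B: Day 10, ANC 800, 38.6°C, neutropenia the only toxicity, G-CSF given.** The 8.2 row is met. Lenalidomide doses are withheld, but the dose level may be kept. The 8.3 row still takes anakinra/placebo down one level. The order of dose reduction is reversed with no temperature gap involved, so aligning the fever cut-offs alone would not cure the problem.

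**Case C: as B, without G-CSF.** Both drugs go down one level. This is not counted as a contradiction (see the objection).

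**Does section 8.11 restore the order at the next cycle?** It lowers lenalidomide if dosing was omitted for the rest of the previous cycle, or if the new cycle is delayed for toxicity newly met on Day 1. In Case A lenalidomide was never omitted. If ANC is back to 1500 by Day 1 and the other start criteria are met, neither condition applies, yet anakinra/placebo is still reduced. In Case B, with lenalidomide resumed within the cycle at the same level, the first condition does not apply either.

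**Size of one reduction step.** Section 8.1 takes anakinra from daily to every other day. In a 28-day cycle that is 28 to 14 injections, (28 − 14)/28 = 50%. This applies if phase II starts at the daily dose, which section 7.12 leaves to the phase I results.

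**The case against.** A DLT definition and a dose-modification trigger serve different purposes, so different temperatures are not in themselves an error. Section 8.2 applies CTCAE unless otherwise specified, and 38.5°C may be such a specification. The opening sentence also covers Case A: an investigator who follows it would turn to lenalidomide first whatever the row says. Both points are fair. They make this an unresolved conflict between sentence and rows, not a fixed instruction to reverse the order. But the protocol does not say which prevails, and section 8.0 makes the table modifications strict in exactly the cycles where tolerance is being learned.

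Several stronger readings are tempting, and the documents do not support them.

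- **That three different ANC cut-offs are in use.** Sections 7.22 and 8.3 agree on ANC below 1000. The lenalidomide row is the outlier because it gives none. The restart conditions do differ.
- **That reducing both drugs together (Case C) breaks the order.** The sentence concerns reducing one drug and not the other. Reducing both need not breach it.
- **That neutropenia without fever is a contradiction.** It is an omission. Section 8.2 has no in-cycle lenalidomide row for it, although platelets have one. Section 8.11 partly covers it by requiring ANC of at least 1500 to start a cycle, and section 4.0 schedules the blood counts.

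**Conclusion.** The contradiction stands. Followed as written, the rows in 8.2 and 8.3 can reduce anakinra/placebo and leave the lenalidomide dose unchanged for a neutropenic event. This happens in the 0.2°C and 0.5°C windows below 38.5°C, and at or above 38.5°C through the G-CSF option. Each outcome conflicts with the sentence opening both sections, and no precedence is stated.

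The effect is on patient management and, in phase II, on exposure to anakinra in the experimental arm. A reader might go further in two directions.

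- **DLT counts and the MTD.** These are not affected. The febrile event is a DLT on 7.22's own terms whatever the tables then do. The DLT rule belongs to phase I, whose patients go off study treatment under Addendum 5.
- **A count of affected patients or a diluted TTP comparison.** Multiplying the 10% listing by 90 evaluable patients gives 9, but that would count febrile neutropenia of any temperature at a rate taken from a general drug listing. The documents give neither the share inside the windows nor the frequency of G-CSF use. Tables become guidelines after two cycles, and the notes closing section 8 allow re-escalation at the investigator's discretion. The loss of exposure is possible but cannot be sized.

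The conclusion assumes that Grade 3 has the same meaning in 7.22 and 8.3, and that the 8.2 table has no further neutropenia row.

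**What to change.** Reconcile sections 7.22, 8.2 and 8.3 before phase II patients are treated under them:

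1. Define febrile neutropenia consistently across the three places (ANC, grade and temperature), or state that the lenalidomide trigger is meant to differ.
2. Make the row actions in 8.2 and 8.3, including the G-CSF option, agree with the order-of-reduction sentence; or reword that sentence and say whether it or the rows prevail.
3. State how lenalidomide is handled within a cycle for Grade 4 neutropenia without fever.

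The study team must choose the clinical thresholds and actions; none is proposed here. The cost is amendment wording. No tests are added, because the blood counts are already in the schedule.

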8.3 Dose Modifications of Anakinra/Placebo during a Cycle of Therapy

Dose reductions of one drug and not the other may be done at the investigators discretion based on attribution of adverse events except neutropenia in which lenalidomide should be decreased first before anakinra.

CTCAE System/organ/Class (SOC)	ADVERSE EVENT	AGENT	ACTION ** (each cycle)
Blood and lymphatic system disorders	Febrile Neutropenia \geq Grade 3	Anakinra/ Placebo	For ANC <1000, omit anakinra/placebo until ANC \geq 1500. Then restart anakinra or placebo with the dose reduced one dose level.
Infections and Infestations	Infection/Febrile Neutropenia \geq Grade 2		Omit until infection resolved; then restart at same dose
	Infection/Febrile Neutropenia \geq Grade 3		Omit until infection resolved; then restart anakinra or placebo with the dose reduced one dose level
Other non-hematologic adverse event	Any adverse event \geq Grade 3		Omit until toxicity reduces to \leq grade 2; then restart anakinra or placebo with the dose reduced one dose level

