8.1 Dose Levels (Based on Adverse Events in Tables 8.2)

Dose Level	Lenalidomide
Starting Dose	25 mg days 1-21 every 28 days
-1	15 mg days 1-21 every 28 days
-2	10 mg days 1-21 every 28 days
-3	5 mg days 1-21 every 28 days

Dose Level	Anakinra
Starting Dose	100 mg SQ daily
-1	100 mg SQ every other day
-2*	100 mg SQ every 3rd day

*If patients unable to tolerate -2 they will go off treatment to event monitoring

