- 15.35 **Pharmacokinetic information:** The absolute bioavailability of Kineret after a 70 mg subcutaneous bolus injection in healthy subjects (n = 11) is 95%. In subjects with RA, maximum plasma concentrations of Kineret occurred 3 to 7 hours after subcutaneous administration of Kineret at clinically relevant doses (1 to 2 mg/kg; n = 18); the terminal half-life ranged from 4 to 6 hours. In RA patients, no unexpected accumulation of Kineret was observed after daily subcutaneous doses for up to 24 weeks. The influence of demographic covariates on the pharmacokinetics of Kineret was studied using population pharmacokinetic analysis encompassing 341 patients receiving daily subcutaneous injection of Kineret at doses of 30, 75, and 150 mg for up to 24 weeks. The estimated Kineret clearance increased with increasing creatinine clearance and body weight. After adjusting for creatinine clearance and body weight, gender and age were not significant factors for mean plasma clearance.
Patients With Renal Impairment: The mean plasma clearance of Kineret in

subjects with mild (creatinine clearance 50-80 mL/min) and moderate (creatinine clearance 30-49 mL/min) renal insufficiency was reduced by 16% and 50%, respectively. In severe renal insufficiency and end stage renal disease (creatinine clearance <30 mL/min), mean plasma clearance declined by 70% and 75%, respectively. Less than 2.5% of the administered dose of Kineret was removed by hemodialysis or continuous ambulatory peritoneal dialysis. Based on these observations, a dose schedule change should be considered for subjects with severe renal insufficiency or end stage renal disease.

Patients with Hepatic Dysfunction: No formal studies have been conducted examining the pharmacokinetics of Kineret administered subcutaneously in patients with hepatic impairment.

15.36 Potential Drug Interactions (USPI Section Drug Interactions):

Warnings and Precautions

Serious Infections – Kineret has been associated with an increased incidence of serious infections (2%) vs Placebo (<1%) in clinical trials in RA.

Administrations of anakinra should be discontinued if a patient develops a serious infection. Treatment should not be initiated in patients with active infections. The safety and efficacy of anakinra in immunosuppressed patients or in patients with patients with chronic infections have not been evaluated.

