Drugs that affect the immune system by blocking TNF have been associated with an increased risk of reactivation of latent tuberculosis (TB). It is possible that taking drugs such as anakinra that blocks IL-1 increases the risk of TB or other atypical or opportunistic infections. (Section 5.1 of the USPI)

Hypersensitivity reactions – Hypersensitivity reactions, including anaphylactic reactions and angioedema have been reported with anakinra. If a severe hypersensitivity reaction occurs, administration of anakinra should be discontinued and appropriate therapy initiated. (Section 5.3 of the USPI)

Immunosuppression – The impact of treatment with anakinra on active and / or chronic infections and the development of malignancies is not known. (Section 5.4 of the USPI)

15.37 Known potential toxicities:

>10% of patients:

Local: Injection site reaction (majority mild, typically lasting 14-28 days, characterized by erythema, ecchymosis, inflammation, and pain). Infection (Upper respiratory infections were 14% in the combined studies while serious infections were only 2%).

1% to 10% of patients: Hematologic: neutropenia

Miscellaneous: Headache, Immunogenicity to Anakinra.

<1% of patients (limited to important or life-threatening):

Hypersensitivity reactions (including anaphylaxis, angioedema, pruritus, rash, urticarial)

15.38 Drug procurement: As of October 31, 2018. Available from commercial supply. Note: Previously provided by SOBI, AB.

15.39 Nursing Guidelines:

- 15.391 Instruct patients on self-administration of anakinra and monitoring of injection sites. Be sure to instruct patient on rotating injection sites - injection sites should be at least 1 inch away from previous injections.
- 15.392 Allow solution to warm to room temperature over 60-90 minutes. Do not shake.
- 15.393 Patients should not receive live vaccines while on agent.
- 15.394 Instruct patient about injection site reactions which can last anywhere from 14-28 days. Instruct patient to contact PI if they have concerns about injection site reactions.
- 15.395 Warn patients of infection risk. Instruct patients to report any fever, or other signs/symptoms of infection to the study team.
- 15.396 Patients may experience headache. Treat symptomatically and monitor for effectiveness.
- 15.397 Although less common, gastrointestinal side effects (diarrhea and nausea), may be seen. Treat symptomatically and monitor for effectiveness.

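### Section 8.3 has no hypersensitivity row, so in Phase II a Grade 3 or higher reaction leads to an anakinra/placebo restart, where Section 15.36 says to discontinue after a severe one

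*Combined protocol and SAP*

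**What the plan says.** **Section 8.3 (anakinra/placebo).** The table has rows for febrile neutropenia, for infection, and for any other non-hematologic event of Grade 3 or higher. There is no allergy row. The last row omits the drug until the event is down to "grade 2; then restart anakinra or placebo with the dose reduced one dose level".

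**Section 15.36 (anakinra warnings).** On hypersensitivity: "If a severe hypersensitivity reaction occurs, administration of anakinra should be discontinued and appropriate therapy initiated". On infection: "Administrations of anakinra should be discontinued if a patient develops a serious infection".

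**Section 8.0 (force of the tables).** "Strictly follow the modifications in this table for the first" two cycles. "Thereafter, these modifications should be regarded as guidelines".

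**Section 8.1 (levels).** The anakinra levels are 100 mg daily, 100 mg every other day, and 100 mg every third day. Patients who cannot tolerate the lowest level "they will go off treatment to event monitoring". Section 7.12 leaves the Phase II dose to the Phase I result.

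**Infection rows of 8.3.** For Grade 2 or higher, with no upper limit: "Omit until infection resolved; then restart at same dose". For Grade 3 or higher: "Omit until infection resolved; then restart anakinra or placebo with the dose reduced one dose level".

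**Section 8.2 (lenalidomide).** This table does have an allergic-reaction entry: interrupt and restart lower after Grade 2-3, discontinue at Grade 4.

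**The concern.** Anaphylaxis and angioedema are listed anakinra risks (15.36, 15.37). The table that a physician is told to follow strictly in cycles 1-2 has no instruction specific to them, and its residual row leads to giving the drug again. The only text that addresses the event directly is in the drug-information section, and it points the other way.

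This looks like an omission. The lenalidomide table and the dexamethasone table (8.4) each name at least one event for which the drug is stopped for good; 8.3 names none. At stake is re-exposure of a patient who has just had a severe reaction, at the same amount per injection. Section 15.39 has patients instructed to self-inject. Phase I patients are off study treatment under Addendum 5, so the practical scope is Phase II.

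**Working it through.** No figure in the plan needs reproducing. The check sets the sections side by side, then counts injections.

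**1. Which row applies?** A hypersensitivity reaction is neither febrile neutropenia nor infection. In 8.3 only the residual row is left, and it covers all non-hematologic events from Grade 3 upward without exception.

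**2. Does the answer depend on what severe means?** Section 15.36 does not tie the word to a CTCAE grade. If it means Grade 3 or higher, the two sections conflict at Grades 3 and 4. If it means only Grade 4, they conflict at Grade 4. The residual row restarts in both cases, so the conflict holds on either reading.

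**3. Which section prevails?** No text says. Section 8.0 speaks of a table in the singular; I take it to cover all the Section 8 tables. On that reading 8.3 is strict for 2 x 28 = 56 days and a guideline afterwards.

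**4. Do other clauses settle it?** The discretion clause in 8.3 concerns which drug to reduce, by attribution. Section 13.22 allows treatment to end for unacceptable toxicity, but does not direct that anakinra be stopped. The 8.1 footnote applies only at the lowest level. None tells the physician to stop anakinra after a severe hypersensitivity reaction.

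**5. What does a restart one level lower mean?** Injections per 28-day cycle, each 100 mg:

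- Daily: 28 (2,800 mg).
- Every other day: 28/2 = 14 (1,400 mg).
- Every third day: 10 if the first falls on Day 1 (Days 1, 4, ..., 28), or 9 if it falls on Day 2 or 3 (1,000 or 900 mg).

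By possible Phase II dose, the 8.3 restart gives:

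- Daily: 28 becomes 14.
- Every other day: 14 becomes 9 or 10.
- Every third day: no lower level is listed, so the 8.1 footnote and the note after 8.4 on further reductions apply instead.

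Discontinuation under 15.36 gives 0 in every case.

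**6. How often?** The documents give no rate for the three-drug combination. Section 15.37 lists hypersensitivity under 1% for anakinra, in a list that also includes pruritus and rash. Section 16.12 plans 45 + 5 = 50 patients per arm. If 1% is taken as a ceiling and assumed to carry over, the expected count in the anakinra arm is below 50 x 0.01 = 0.5, and the chance of at least one case is below 1 - 0.99^50 = 0.395. Severe reactions would be a subset.

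**The case against.** The strongest reply is that the right instruction is already in the protocol. Section 15.36 names the event and 8.3 does not; reading a specific warning over a residual row is natural, and 13.22 lets a physician stop. This stands in part: many physicians would stop anakinra, and nobody can say that a patient would certainly be re-exposed. But 15.36 is drug information, no text ranks it above 8.3, and 8.0 demands strict adherence to the table in the period concerned.

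A second reply is rarity. It bears on priority, but does not remove a safety conflict that is cheap to correct.

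A reader might infer three stronger points that the documents do not support:

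- **That the infection rules contradict each other outright.** Both sections stop the drug during infection. They conflict only if 15.36 means permanent discontinuation. The definition of discontinue under 8.4 governs the Action column of the dose tables, not 15.36. Section 10.12 also separates severe from serious events, so Grade 3 or higher is not the same as serious.
- **That the overlapping infection rows leave the dose undetermined.** A Grade 3 infection literally meets both rows, but the intent is clear: same dose after Grade 2, reduced dose from Grade 3. This is a drafting slip.
- **That the patient would return to the full schedule.** The note after 8.4 allows re-escalation only at the investigator's discretion, after a cycle with no further event above Grade 2, and for a reduction made at the start of a cycle. A return from 14 to 28 injections is possible under a daily Phase II dose, but would need a deliberate choice.

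**Conclusion.** The conflict is real for hypersensitivity. As written, 8.3 restarts anakinra/placebo after a reaction for which 15.36 calls for discontinuation, and the table is strict for the first 56 days. If the Phase II dose is daily or every other day, the difference is 14, or 9-10, injections of 100 mg per cycle against none. If it is every third day, no lower level exists and the restart rule does not operate in the same way.

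The conclusion rests on two readings: that 8.0 covers the 8.3 table, and that a hypersensitivity reaction belongs in its residual row. It does not rest on an assumed event rate, and no patient count is claimed. It should be corrected before Phase II dosing.

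**What to change.** Add an immune-system row to 8.3: discontinue anakinra/placebo for an allergic or hypersensitivity reaction of Grade 3 or higher, or any anaphylaxis, at least possibly related to anakinra/placebo. Exclude these events from the residual row. The row should name the blinded product, so that it applies to both arms without unblinding. Copying the Grade 4 threshold from the lenalidomide table would not be enough, because Grade 3 reactions would stay in the restart row.

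As a wording correction, limit the first infection row to Grade 2. Ask the sponsor to state whether 15.36 allows the restart in 8.3 after a serious infection has resolved. I would not write restart permission into 15.36 here: that section cites the product label, which cannot be checked from these documents. If the sponsor adds a separate Grade 4 infection rule, the existing Grade 3 or higher row must be capped at Grade 3, or the overlap returns.

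The cost is amendment wording: one new row, one exclusion and one grade limit, plus the sponsor's answer on infection. The downside is slightly less anakinra exposure in a few patients. They stay on study unless all agents are stopped (note after 8.4) and remain evaluable for the primary endpoint (16.11). The target of 45 evaluable patients per arm and the one-sided 0.05 level do not change.

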NOTE: If the patient experiences a significant adverse event requiring a dose reduction at the start of the next cycle, then the dose will remain lowered for that entire subsequent cycle. If that cycle is

completed with no further adverse events >Grade 2, then the dose may be increased, at the investigator's discretion, one level at a time, in the following cycles.

NOTE: Adverse events requiring a dose-reduction step for any or all drugs beyond the two dose-reduction steps (levels –1 and –2) will be at the discretion of the treating physician, if the decision is made for the patient to be kept on study. These dose reductions must be clearly recorded in reported clinical data.

NOTE: Patients in whom one or more of the study treatment agents have been discontinued will remain on study unless all study treatment agents are discontinued. Patients in whom all study treatment agents were discontinued will proceed to event monitoring (see [Section 18.0](#)).

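### Table 8.3 has no hypersensitivity row, so its catch-all restart rule conflicts with the instruction in 15.36 to discontinue anakinra after a severe reaction

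*Combined protocol and SAP*

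**What the plan says.** **Section 8.3 (anakinra/placebo).** The table covers febrile neutropenia, infection, and a residual row for any other non-hematologic event of Grade 3 or higher. No row names an allergic reaction and no row says to discontinue. The residual row ends with "grade 2; then restart anakinra or placebo with the dose reduced one dose level".

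**Section 8.1 (dose levels).** Anakinra starts at 100 mg daily, level -1 is "100 mg SQ every other day", and level -2 is 100 mg every third day. The footnote to level -2 reads "If patients unable to tolerate -2 they will go off treatment to event monitoring".

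**Section 8.0 (force of the tables).** Staff are told: "Strictly follow the modifications in this table for the first" two cycles. After that, "Thereafter, these modifications should be regarded as guidelines to produce mild-to-moderate, but not debilitating, side effects".

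**Section 15.36 (anakinra warnings).** "If a severe hypersensitivity reaction occurs, administration of anakinra should be discontinued and appropriate therapy initiated".

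**Section 8.2 (lenalidomide).** This table does have an allergy row, "Allergic reaction Grade 2-3", followed by a Grade 4 row that discontinues lenalidomide.

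**Notes after Section 8.4.** The second note leaves reductions beyond level -2 to the treating physician if the patient is kept on study. The third says "Patients in whom one or more of the study treatment agents have been discontinued will remain on study", unless every agent has been stopped.

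**The concern.** Two current instructions apply to the same event and point in opposite directions. The one that staff would normally open when deciding the next dose is the less cautious one.

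What is at stake is the safety of an individual patient. Section 15.37 lists anaphylaxis and angioedema among the important or life-threatening reactions to anakinra. The only condition for restart in the catch-all row is that the reaction has settled to Grade 2 or lower, which says little about what the next injection might do. Under 15.391 patients are taught to inject themselves, and Table 8.3 does not ask for a supervised restart.

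**Working it through.** No formula applies to the main question, and the plan gives no figure to reproduce. The check sets the sections side by side.

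1. **Which row applies?** Table 8.3 has no allergy row, so a Grade 3 or higher allergic reaction on anakinra/placebo lands in the residual row. That row has no upper grade limit.

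2. **Are the two actions really different?** Yes. The definitions after 8.4 treat omitting as skipping doses and discontinuing as stopping the drug completely. The catch-all row omits and restarts; 15.36 discontinues.

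3. **Does the meaning of severe matter?** The protocol does not tie the word to a CTCAE grade. If it means Grade 3 or higher, the two rules conflict at Grades 3 and 4. If it means Grade 4 only, they still conflict at Grade 4, by step 1.

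4. **What happens at each dose level?**

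| Level when the reaction occurs | Table 8.3 with 8.1 | 15.36 |
|---|---|---|
| Daily | Omit, then every other day | Discontinue |
| Every other day | Omit, then every third day | Discontinue |
| Every third day | No lower level; off treatment if not tolerated (8.1 footnote), but further reduction at the physician's discretion (second note after 8.4) | Discontinue |

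   The first two lines are a plain conflict. The third is less clear, because the footnote and the note do not say quite the same thing.

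5. **Does the reduction lower the dose at re-exposure?** No. The change per injection is 100 mg - 100 mg = 0 mg. Only the interval lengthens.

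6. **When does the table bind?** Strictly in Cycles 1 and 2. From Cycle 3 it is a guideline, though it still points away from 15.36.

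7. **How often might this arise?** Section 15.37 gives less than 1% for all hypersensitivity, including pruritus and rash. If that figure carried over to this three-drug regimen, which is an assumption, the 45 evaluable patients planned for the experimental arm would yield fewer than 45 x 0.01 = 0.45 expected cases of any severity. The documents give no rate for severe reactions or for restarts after them, so the event at issue cannot be quantified further.

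8. **Who is affected?** Phase II only. Under the note in Section 13.0, phase I patients have gone off study treatment. The phase II schema still gives anakinra availability as to be determined, and 7.12 leaves the dose to the phase I results.

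**The case against.** The strongest reply is that the needed instruction is already in the protocol. Section 15.36 names this event, while the row in 8.3 is residual, and it is ordinary practice to let a specific sentence govern a general one. Other provisions support stopping: 13.22 ends treatment for unacceptable toxicity, the third note after 8.4 expects single agents to be stopped while the patient stays on study, and 7.7 tells staff in an after-hours emergency to assume active treatment.

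Much of this stands. A reader might infer that the protocol obliges staff to give another injection, or that it contains no rule for severe hypersensitivity. The documents support neither reading: 15.36 is part of the protocol, and an investigator who reads it has a clear instruction to stop. Re-exposure could happen if only the table is read; it is not what the document as a whole requires.

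The reply does not remove the conflict. No section gives 15.36 precedence, and Table 8.3 does not refer to it. Section 13.22 and the third note permit a stop but do not direct one for this event. The discretion sentence at the head of 8.3 concerns which drug to reduce, not whether to stop for good. Meanwhile 8.0 asks for strict use of the tables when tolerance is still unknown.

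A further fair point is that lenalidomide can also cause hypersensitivity (15.17) and has its own row in 8.2. A new anakinra row therefore needs an attribution condition.

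**Conclusion.** The conflict is real and should be corrected before phase II dosing. Table 8.3 sends a Grade 3 or higher allergic reaction on daily or every-other-day anakinra/placebo to a restart at an unchanged 100 mg per injection, while 15.36 calls for discontinuation. At every third day the position is less clear-cut.

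The reach is small. The event is rare, only phase II is concerned, and the table is strict for two cycles only. The reason to act is the possible severity of a repeat reaction, not its frequency. A reader might infer some threat to the trial's results; there is none, since the time-to-progression endpoint, the sample size and the planned analysis are untouched.

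The conclusion assumes that severe means Grade 3 or higher. It survives a Grade 4 reading, with fewer events covered.

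**What to change.** Add a row to Table 8.3: *Severe hypersensitivity or allergic reaction (grade to be set by the sponsor, for example Grade 3 or higher), at least possibly related to anakinra/placebo: discontinue anakinra/placebo and start appropriate treatment.* Exclude these events from the catch-all row. Do not copy the lenalidomide row from 8.2, which allows a restart after a first Grade 2-3 allergic reaction.

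The cost is one row and one exclusion phrase in an amendment, with no change to tests, patient numbers or analysis. There is a small downside. Because treatment is blinded and lenalidomide can cause similar reactions, some patients may stop anakinra/placebo for a reaction due to another drug. Under the third note after 8.4 they stay on study as long as at least one agent continues.
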